## **2.2 Previous Data**

A 2012 Cochrane review identified six efficacy trials (n=804) and observed a pooled 64% reduction in fracture risk from these exercise programs (9). Each of the six interventions included a combination of strength, aerobic, and balance exercises plus an individual who played a coaching roll (10), working closely with subjects to encourage adherence and help overcome barriers to participation. A great number of clinical trials for exercise promotion (e.g., LIFE Trial) have included “coaching,” typically from a research assistant (16) being integrated into medical care, due to financial incentives for population health management in the Affordable Care Act (ACA)(18). Health Dialog is one of the largest US companies doing this coaching, also called “care management.” In 2010, Health Dialog completed a randomized trial of 174,120 subjects, published in the *New England Journal of Medicine*, showing that telephone care management reduced hospitalizations (19).

## **2.3 Study Rationale**

Physicians and patients need options for preventing the consequences of osteoporosis. The most feared complication of osteoporosis is a fragility fracture (FF), which often precipitates disability, nursing home admission and death (2, 3). The need for treatment options is exacerbated by the striking reduction in use of bisphosphonates, due to fear of adverse events, leaving many patients untreated. In addition, two of the top 100 Priority Topics for Comparative Effectiveness Research from the Institute of Medicine are relevant to this question: “*Compare the long-term effectiveness of weight-bearing exercise and*

*bisphosphonates in preventing hip and vertebral fractures in older women with osteopenia and/or osteoporosis” and “Compare the effectiveness of primary prevention methods, such as exercise and balance training, versus clinical treatments in preventing falls in older adults at varying degrees of risk.”*

The \$30 Million PCORI-funded falls prevention trial tests a different, yet complementary, intervention. PCORI is now conducting a 6000-person study of a falls care manager to reduce fall-related injuries, by focusing on using therapy services (e.g., vision, PT/OT). This is very different – yet complementary – to the 450 hours of exercise programming supported by 90 exercise coaching contacts in the study proposed here. Another difference is that exercise coaching has the potential to improve a key patient-centered outcome – loneliness – through the use of group-based exercise. The difference between the interventions can be seen in the proposed effect size. The PCORI falls care manager trial requires 6000 seniors to detect an effect on fall-related injury, though the study we propose needs only 2000 seniors, as the studies show that exercise interventions supported by a coach reduce fractures by 2/3 (9). If both studies prove effective, it will provide seniors with two complementary choices. Patients may benefit from such therapy services before or during exercise coaching, to overcome barriers to exercise.

Policy changes are best informed by large-scale effectiveness trials. Medicare currently pays for cardiac rehabilitation, which took years and numerous large-scale studies to provide sufficient evidence to allow its approval. There is no other common disease complication that appears to be more preventable with physical activity than FF, yet the evidence is based solely on six small studies (total N=810) (9). This study has been designed, from the beginning, to inform policy decisions by 1) being large enough to impact a key clinical outcome (FF) that patients care deeply about, 2) adhering to pragmatic trial design principles (31) and 3) involving a care management provider (Health Dialog), so that the findings can be rapidly disseminated as a service offered to health plans and Accountable Care Organizations (ACOs).

There will be three organizations (Penn State Hershey, University of Pittsburgh, and Temple University) that will carry out identical intervention procedures, including participant recruitment, DXA scans, stakeholder engagement, recruiting community sites, training group leaders, implementation planning with the PCPs, intervention delivery, outcomes assessment, and provision of feedback to the referring physicians. Each site is recruiting a different number of subjects, based on the difference in the populations seen at those centers (e.g., Temple is the lowest, UPMC is the highest). No patients will be enrolled at Johns Hopkins.

Johns Hopkins University will contribute two Co-Investigators, [name], [name] [name]. They will be involved in various leadership committees and managing the DXA data. They will not see subjects though will have access to *Protected Health Information* (PHI).

Additional coordination and oversight by Penn State Hershey:

The Penn State research staff include a “Core” group, including the study’s Principal Investigator, Project Manager, and Exercise Physiologist. Each research site (Penn State Hershey, Pittsburgh, Temple) has a Site Principal Investigator, Site Project Manager, and one or more Exercise Coaches. The Core Project Manager is responsible for overseeing all Site Project Managers. The Core Exercise Physiologist is responsible for overseeing all Exercise Coaches.

The lead investigative team (which includes the core Principal Investigator (PI), core project manager, core exercise physiologist, all site PIs – from Penn State, Pittsburgh, Temple, and Johns Hopkins – and all site project managers, meet on a weekly basis. Site PIs will review and update the core PI on the study’s progress at their site. Each quarter, the core project manager will visit or remotely monitor each of the research sites (Pittsburgh and Temple) to audit a set number of research files, for completion and accuracy. The core project manager will also audit a number of phone interviews and a number of face

to face meetings between research staff and participants to assure that protocols are being followed equally across sites.

In addition to the core project manager, the core exercise physiologist will perform travel visits at all three locations (Pittsburgh, Temple, and Penn State) to oversee the exercise intervention, and will work closely to the coaches at each research institution. Table 1 clarifies the group leaders and coaches' responsibilities.

**Table 1. Group leaders vs coaches responsibilities.**

Person	Responsibilities
Group Leader	Lead exercise class
Exercise Coach	Phone calls to participants Exercise prescription/modification Data entry/tracking Supervise/observe group leaders

To prevent any confusion during this review, we have decided to define our study subjects (Table 2).

**Table 2. WISE Study Subjects**

Subjects	Description
Participants	Individual 65 years or older who have had a fragility fracture in the past 10 years
Group leader	Members of the community who are willing to lead exercises at least once a week.
Community members	Members of the community who would like to participate in the exercise program but will not have access to exercise coaching.
Spanish Speaking Interview Group	Members of the community who are willing to participate in an individual interview and provide feedback to study staff regarding the Spanish version of the program

The recruitment for the exercise site locations are already approved under the quality improvement project, "Peer-led Strength Training Program for Older Adults", IRB# 40418NR.

## **3.0 Inclusion and Exclusion Criteria**

### **3.1 Inclusion Criteria**

#### Group Leaders

- ≥ 21 years old
- Fluently read and speak English
- Willing to lead sessions three times a week for most weeks for the next 36 months or to the end of the study, whichever comes first

#### Participants

- ≥ 65 years old
- Previous Fragility Fracture (FF) in past 10 years.
- Able to speak and understand English.
- Patients will need to be willing to try exercising and agree to annual follow-up measurements

#### Community Members

- Able to speak and understand English.
- ≥ 18 years old

#### Spanish Speaking Interview Group

- Fluently read and speak Spanish
- ≥65 years old

### **3.2 Exclusion Criteria**

#### Group Peer Leaders

- If the group leader's blood pressure reading is ≥180 systolic or ≥110 diastolic OR heart rate is ≥ 120 bpm
- If the answer to the following questions are "yes", we will exclude the participant from the study
  - Have you ever been told by a health professional that you should not exercise OR exercise only when supervised by a professional?
- Unable to walk 100 feet without using any special equipment, such as a walker, or a wheelchair
- Unable to obtain PCP's consent
- If they answer "NO" to the following question
  - Is it OK if we contact your PCP?
- Plans to move in the next 36 months
- Pregnant or planning to become pregnant in next 36 months
- Currently enrolled in the WISE Study as a participant as defined in section 3.1 of this protocol

#### Participants

- If the participant's blood pressure reading is ≥180 systolic or ≥110 diastolic OR heart rate is ≥ 120 bpm
- If the answer to the following questions are "yes", we will exclude the participant from the study
  - Have you ever been told by a health professional that you should not exercise OR exercise only when supervised by a professional?
- Unable to walk 100 feet without using any special equipment, such as a walker, or a wheelchair
- Unable to obtain PCP's consent
- If they answer "NO" to the following question
  - Is it OK if we contact your PCP?
- Planning on moving out of the area in the next 36 months
- Has ever participated in the Band Together exercise program
- Positive Callahan cognition screener: If participant fails 2 questions, research coordinator will explain study in detail and ask read-back questions. Exclude participant if failed read-back.
- Participating in research involving strength, balance, or aerobic exercise
- No more than one person per household can participate
- If participant lives in Lebanon County (except Palmyra – zip code 17078)

#### Community Members

- If the answer to the following questions are "yes", we will exclude the participant from the study
  - Have you ever been told by a health professional that you should not exercise OR exercise only when supervised by a professional?
  - Are you currently enrolled in the WISE study as a participant?
- Unable to walk 100 feet without using any special equipment, such as a walker, or a wheelchair

- Unable to obtain PCP's consent
- If they answer "NO" to the following question
  - Is it OK if we contact your PCP?

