**Ineligible participants will be asked if they would be interested in being group leaders for the study.**

### **3.3 Early Withdrawal of Subjects**

#### **3.3.1 Criteria for removal from study**

It is possible we will withdrawal participants from the study if they become injured and cannot exercise or if they are asked by their Primary Care Provider to suspend exercise. The Principal Investigator reserves the right to remove a participant from the study for any reason, based on their discretion.

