#### Community Members

Community members will be people living around our exercise sites. They will be identified by our exercise sites and our participants. They may be, but not limited to, parishioners of a church that hosts our program, members of the senior center hosting our program, control and intervention participants who have completed the WISE study, or a family member or friend of a current participant.

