#### **Group A: Control Group- *Enhanced Usual Care Intervention***

Research staff will review the three printed pamphlets on fall risks and exercising during baseline. We will recommend the control group to exercise. However, they will NOT be able to participate in our exercise program intervention. Control group participants will receive information about exercise from the Centers for Disease Control and newsletters about fall prevention that include exercise. They are encouraged to exercise, though they are not invited to Band Together, nor will they receive one-on-one support from our coaches. We will not ask people to abstain from any form of exercise.

In addition, to enhance the usual care intervention and maximize patient safety, the baseline bone density results (measured by Dual-energy X-ray absorptiometry, DXA) will be communicated to their PCP, and any *critical* values of a baseline measure (e.g., Blood pressure, Depression screen) to both the patient and primary care provider.

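### The group-leader and community-member screens ask only about current enrolment, so they do not fully enforce the bar on controls for withdrawn controls or controls' housemates

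*Combined protocol and SAP*

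**What the plan says.** All references are to the combined protocol and SAP.

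- **Bar on controls.** Section 7.2.6.3 (Group A) says of the control group that "they will NOT be able to participate in our exercise program intervention". It gives no end date and does not mention withdrawal or household members.
- **Screens for the non-randomised roles.** In section 3.2, group leaders are excluded if "Currently enrolled in the WISE Study as a participant as defined in section 3.1 of this protocol". Community members are asked "Are you currently enrolled in the WISE study as a participant". Neither list has a household criterion.
- **Household rule.** Section 3.2 (Participants) states "No more than one person per household can participate". It applies to trial participants only.
- **People screened out.** Section 3.2 ends with "Ineligible participants will be asked if they would be interested in being group leaders for the study", and section 4.2 repeats the offer. Neither makes an exception for someone excluded only by the household rule.
- **Sources of community members.** Section 4.1 gives an open-ended list that includes "control and intervention participants who have completed the WISE study, or a family member or friend of a current participant". The family-and-friend source is not limited by arm. Section 7.2.4 also recruits through participants' personal contacts.
- **Withdrawal.** Section 3.3.2 withdraws a participant as soon as the person asks, and sets no later bar.
- **What community members receive.** Section 7.2.6.3 lists the leader-led classes, Zoom sessions, exercise trackers and, where needed, bands and a tablet. It does not give them an exercise coach.

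**The concern.** The bar on controls should hold for the whole 36 months over which their events are counted. The two screens that guard the other entrances test enrolment status on the day of screening. They do not test whether the person was randomised to control, or lives with someone who was.

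Two openings follow. A control who withdraws is no longer currently enrolled and so passes that criterion. A control's housemate, turned away as a second participant from one household, falls within the group to be invited to lead, and may also qualify as family for a community place.

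Either opening could expose controls to part of the exercise program. For controls whose injuries are still counted, that would tend to move the control rate towards the exercise rate. The first also makes leaving the trial a way into the classes, an incentive that exists in one arm only.

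**Working it through.** **1. The text, route by route**

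*Withdrawn control.* Withdrawal takes effect on request (3.3.2), so the current-enrolment criterion no longer applies (3.2). Sections 4.1, 7.2.4 (Community Members) and 7.2.4 (Group leaders) name former participants as a source only when they have completed. The list in 4.1 is expressly not exhaustive, however, and no exclusion requires completion. The route is therefore not offered, but it is not closed either. Before any session the person needs physician permission (7.2.5) and written consent (5.2.1). A leader also needs blood pressure screening and the 8-hour training (7.2.3, 7.2.6).

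*Control's housemate.* The household rule makes this person an ineligible participant, the closing line of 3.2 directs staff to ask about leading, and the leader exclusions do not mention household. Section 4.1 separately admits family without regard to arm. The control still may not attend, so any exposure is indirect, through materials or sessions used at home.

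**2. The plan's own power**

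Inputs: 13% control and 7% exercise (1.1); 960 remaining after 15% loss, stated power 87% (8.3); two-sided alpha 0.05 (8.2, 8.3); 1:1 allocation (7.2.6.3), hence n = 480 per arm. With p̄ the mean of the two rates,

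power = Φ{ [ (p1 − p2) − 1.96·√(2·p̄(1 − p̄)/n) ] / √( [p1(1 − p1) + p2(1 − p2)]/n ) }

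- p̄ = 0.10; √(2 × 0.10 × 0.90/480) = 0.01936, and times 1.96 = 0.03795
- √((0.1131 + 0.0651)/480) = 0.01927
- (0.06 − 0.03795)/0.01927 = 1.144, so power = 87.4%, against the stated 87%

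The formula also reproduces the other four rows of the table in 8.3: 71.5%, 90.2%, 54.2% and 53.1%, against 71%, 90%, 54% and 53%.

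**3. Illustration of dilution**

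The documents give no exposure rate and no effect for exposed controls, so both are assumptions. Let c be the share of analysed controls who are exposed and e the fraction of the 6-point benefit they receive. Then control rate = 13% − c × e × 6 points, with the exercise rate fixed at 7% and n = 480.

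| Exposed (c) | Half effect: difference | Half effect: power | Full effect: difference | Full effect: power |
|---|---|---|---|---|
| 0% | 6.0 | 87.4% | 6.0 | 87.4% |
| 5% | 5.85 | 85.9% | 5.7 | 84.3% |
| 10% | 5.7 | 84.3% | 5.4 | 80.8% |
| 20% | 5.4 | 80.8% | 4.8 | 72.2% |

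Differences are in percentage points. The losses hardly depend on the formula. At full effect and 10% exposed, the Schoenfeld log-rank approximation goes from 89.1% to 82.7%, and the continuity-corrected test from 85.0% to 77.7%.

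**The case against.** The strongest reply is that no passage admits a withdrawn control. Former participants are named as a source only once they have completed, and the bar in 7.2.6.3 has no end date, so it can be read as continuing after withdrawal. That reading is reasonable. It does not settle the matter, because the screening criteria that staff apply do not carry it.

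Four stronger inferences are tempting, and the documents do not support them.

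- *A control could leave one day and join the classes the next.* New physician permission and written consent come first. The carry-over of permission in 7.2.5 is for people who completed enrolment and were recently active in Band Together. Leaders must also be trained.
- *An exposed control receives the full tested benefit.* Aim 1 tests coached exercise. Community members have no coach, a late joiner gets only part of 36 months, and housemate exposure is second-hand. Full effect is an upper bound.
- *The number of leader and community places shows how large the problem could be.* Capacity says nothing about uptake by controls or their households. Section 8.1 expects about 15% drop-out, loss and death combined, so if control-arm losses match that, withdrawal alone could not expose 20% of controls.
- *The exposure would necessarily go unrecorded and dilute the result.* Staff screen and consent every leader and community member, so a former control who joined would leave a study record. The record search in 8.2 and 8.3 covers subjects lost to follow-up and does not clearly extend to withdrawals on request. A control censored at withdrawal would not dilute the result through later exposure.

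It is also fair that controls are encouraged to exercise and not asked to abstain, and that the documents never describe the household rule as a protection against contamination. Exercise in general is part of the comparator; Band Together is what 7.2.6.3 withholds.

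**Conclusion.** The gap is real but limited. The screens in 3.2 do not, as written, enforce the bar in 7.2.6.3 over a control's full 36 months, and the closing line of 3.2 and the family source in 4.1 can bring program materials into a control's home. The plan already uses tighter wording elsewhere in 3.2: participants are excluded for any past Band Together participation, and the interview group's exclusion refers to control participants specifically.

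The size is unknown and probably modest. On the illustrative assumptions, the loss of power at half effect is 1.5, 3.1 and 6.6 points for 5%, 10% and 20% of controls exposed. At full effect it is 3.1, 6.6 and 15.2 points. These figures apply only to exposed controls whose events remain in the analysis. For those who withdraw and are not followed, the issue is instead an incentive to leave in one arm. Section 8.3 calls the trial over-powered, but its own table gives 71% if the exercise rate is 8%, so a cheap protection is worth having.

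**What to change.** - **Section 3.2, group leaders and community members.** Keep the current-enrolment criterion and add: not eligible if ever randomised to control, or living with a control participant, until that control's 36-month date has passed, whether or not that control has withdrawn.
- **Section 4.1 and the closing line of section 3.2 (with its repeat in 4.2).** Limit the family source and the invitation to lead in the same way, so that a control's housemate is not approached during that period.
- **Screening.** Add one question on household and check each applicant against the allocation list. Apply the check once to leaders and community members already admitted.
- **Recording.** Record any control found to have been exposed, with dates, so that the extent can be reported.

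The cost is a short amendment to the screening forms and the loss or delay of a few volunteers who are not randomised. Completers past month 36 are unaffected, and neither the sample size nor alpha changes.

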#### Spanish Speaking Interview Group

- Unable to speak or read Spanish
- Currently enrolled in the WISE Study as a control participant as defined in section 3.1 of this protocol

**Ineligible participants will be asked if they would be interested in being group leaders for the study.**

### **3.3 Early Withdrawal of Subjects**

#### **3.3.1 Criteria for removal from study**

It is possible we will withdrawal participants from the study if they become injured and cannot exercise or if they are asked by their Primary Care Provider to suspend exercise. The Principal Investigator reserves the right to remove a participant from the study for any reason, based on their discretion.

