We will additionally request permission from subjects to access their claims through RESDAC or a similar company and PaTH network. This will allow for comprehensive collection of data for our primary outcome. We will need the participant's health insurance claim (HIC) number for RESDAC.

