#### **3.3.2 Follow-up for withdrawn subjects**

If the participant contacts us that they want to withdraw from the study, we will do so at that time. For the Spanish Speaking Interview Group, we will replace subjects who are withdrawn.

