### **8.2 Sample size determination**

In order to have 95% statistical power to detect a 6% difference in the composite outcome measure of SFRI (including FF) between groups at 36 months follow-up, we will enroll 500 subjects at baseline. We assume a Type 1 error rate (alpha) of 5% (.05), statistical power of 95% (.95), and a two-tailed log-rank test for the time until SFRI (including FF), which allows us to detect significant differences in either direction. We estimate that 15% of subjects will be lost to follow-up at 36 months, as losses to follow-up in studies of older adults tend to be lower (37). Also, for subjects lost to follow-up, we will conduct an electronic health record search, to measure the incidence of FF/SFRI. The study is over-powered for the main outcome measure (SFRI, including FF), in order to (1) provide the possibility of seeing an impact on FF, the most clinically meaningful measure and (2) insuring, given the amount of money spent on the study, that it is powered to observe a clinically meaningful difference even if several of our assumptions are not met.

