### **8.3 Statistical methods**

We will conduct the primary analyses on the main outcome measure, SFRI, including FF. Initially, the two randomized groups will be compared qualitatively on important demographic and other baseline variables to ensure successful randomization. For the primary outcome (SFRI, including FF), we will apply intention to treat (ITT) principles with all available data and the covariates of medical center, age, sex, race and ethnicity, smoking status, education, and anti-osteoporotic medication use included in the primary set of analyses (112, 113). If it is determined that the groups, by chance, are significantly different on other covariates, then we will include those covariates in secondary analyses. Of note, while the original proposed study of 2100 subjects was powered to detect a difference in fragility fractures, the modified sample size of 1130 will be powered only to detect a difference in serious fall-related injuries, of which fragility fracture is only one type. As the rate of fragility fracture is lower than the rate of serious fall-related injury, the study is no longer powered to detect a difference in fragility fracture, yet is powered to detect a difference in serious fall-related injury.

Power Estimates (assuming 15% lost to follow-up, 960 remaining at 3 years).

	Control rate	Intervention Rate	Relative Risk Reduction	Number Needed To Treat	Power
Serious Fall-related injury (BASE)	13%	7%	46%	17	87%
● Scenario 2 (smaller effect)	13%	8%	38%	20	71%
● Scenario 3 (lower rate of FF/SFRI)	12%	6%	50%	17	90%
● Scenario 4 (smaller effect + lower rate of FF/SFRI)	12%	8%	33%	25	54%
Fragility Fracture alone	7%	4%	43%	33	53%

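### Section 3.3.1 lets staff withdraw injured participants from the study, not just from exercise, and no outcome follow-up is provided afterwards, which risks informative censoring that favours the exercise arm

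*Combined protocol and SAP*

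**What the plan says.** Section 3.3.1 gives three grounds for ending participation.

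- Injury: "It is possible we will withdrawal participants from the study if they become injured and cannot exercise".
- PCP advice: "if they are asked by their Primary Care Provider to suspend exercise".
- Discretion: the Principal Investigator "reserves the right to remove a participant from the study for any reason, based on their discretion".

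All three are framed as removal from the study. None is framed as stopping the exercise sessions only.

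Section 3.3.2 is headed as follow-up for withdrawn subjects. For trial participants it says only: "If the participant contacts us that they want to withdraw from the study, we will do so at that time". It is silent on anyone whom staff remove.

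Three other provisions bear on the point.

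- Sections 8.2 and 8.3: "for subjects lost to follow-up, we will conduct an electronic health record search, to measure the incidence of FF/SFRI".
- Section 1.2: "We will additionally request permission from subjects to access their claims through RESDAC or a similar company and PaTH network".
- Section 8.3, on the primary outcome: "we will apply intention to treat (ITT) principles with all available data".

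**The concern.** Under intention to treat, a person who stops exercising stays in follow-up and is analysed as randomised. Section 3.3.1 lets stopping exercise become leaving the study.

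People removed because of an injury or a PCP's concern are plausibly at higher risk of a serious fall-related injury (SFRI) than those who stay. If more of them are removed from one arm, that arm's later events are under-observed and its rate looks lower.

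The triggers are likely to operate mainly in the exercise arm. Under 7.2.6.3, only that arm has a programme, regular coach calls that ask about injuries, check-up calls after missed classes, six-monthly reports to the PCP, and investigator review of a health event before return to exercise. Controls have no coach, and their scheduled outcome contact is the 4-month call in 7.2.7, which both arms receive. An investigator who reviews a return to exercise knows the allocation.

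Ending the calls matters for the primary outcome. Under 1.2, records are sought for events that participants report, and an event needs record evidence to count. Blinded adjudication cannot recover an event that was never collected.

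**Working it through.** **1. The plan's own figure.** Inputs from 8.1 and 8.3: 1130 enrolled, 15% loss, 960 remaining (480 per arm), 13% against 7%, two-sided 5%. Two-proportion power is Φ{[√n·|p1−p2| − 1.96·√(2p̄(1−p̄))] / √(p1(1−p1)+p2(1−p2))}.

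- Numerator: 21.91×0.06 − 1.96×√0.18 = 1.3145 − 0.8316 = 0.483.
- Denominator: √0.1782 = 0.422.
- Φ(1.144) = 87.4%, against the stated 87%. It reproduces.

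The 15% is one pooled rate. It allows for lost numbers, not for loss that differs by arm or is related to risk.

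**2. Which events are exposed.** The planned test is a log-rank test on time to SFRI.

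| Reason for removal | Effect on the primary outcome |
|---|---|
| Disabling injury that is itself an adjudicated SFRI | None: the first event is already counted |
| Injury that does not qualify as an SFRI | A later first SFRI may be missed |
| PCP asks for exercise to be suspended | A later first SFRI may be missed |
| Investigator discretion | A later first SFRI may be missed |

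Fall counts and 36-month outcomes are exposed in every row.

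**3. Size under no true effect.** The documents give no rate of withdrawal for injury, so every input here except the 13% is assumed: 36-month risk 13% in both arms; 20–30% of people frail, with 3–4 times the hazard; 25–50% of the frail and 2–5% of the others removed from the exercise arm at a uniformly distributed time (7–16% of the arm); no removals in the control arm; nothing recovered from records or claims. An exponential frailty simulation over four such settings gave event-rate ratios of 0.975, 0.950, 0.936 and 0.931. The observed exercise-arm proportions were 12.3% down to 11.2%.

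**4. False benefit under the planned test.** With D total events, z = −ln(rate ratio)·√D/2, and the chance of a significant result favouring exercise is about Φ(z − 1.96).

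| Rate ratio | D = 480×(0.13 + observed) | z | Chance of false benefit |
|---|---|---|---|
| 1 | – | 0 | 2.5% |
| 0.975 | 480×0.253 = 121.4 | 0.0253×11.02/2 = 0.14 | Φ(−1.82) = 3.4% |
| 0.931 | 480×0.242 = 116.2 | 0.0715×10.78/2 = 0.385 | Φ(−1.575) = 5.8% |

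**5. The same question on raw proportions, for contrast.** Putting p1 = 13% and p2 = 13%×(1−q) into the formula in step 1, where q is the share of exercise-arm SFRIs uncounted, gives 8.9% at q = 10% and 24% at q = 20%. These figures do not suit this plan. A log-rank test also drops the censored person-time, and the simulated proportions imply q of only 1 − 12.3/13 = 5% to 1 − 11.2/13 = 14%.

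**The case against.** The strongest reply is that the text is milder than it may look. Four stronger readings are tempting, and the documents do not support them.

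- **That withdrawn people get no follow-up at all.** This is not stated. Section 3.3.2 is silent, 8.2 and 8.3 promise a record search, and 1.2 plans a request for claims access. The 15% in 8.1 covers dropout, loss and death, while 8.2 gives the same 15% as loss to follow-up, so the search may be meant to include withdrawn people. However, 8.1 lists dropping out and being lost separately, no section says that staff-withdrawn people are searched, and claims access depends on permission.
- **That injured exercisers are routinely removed, and only exercisers.** Removal is permissive. Section 7.2.6.3 gives a return-to-exercise route after hospitalisation or six weeks' absence, and a home option. The rule refers to participants generally, and controls are also encouraged to exercise. The asymmetry is an inference from how the triggers arise and are detected.
- **That the rule contradicts intention to treat.** The commitment is to all available data, and people can be analysed as randomised up to censoring. The principle is put at risk, not contradicted.
- **That the chance of a false benefit reaches 9–24%.** Those figures compare raw proportions, and the upper one needs more uncounted events than the simulation implies. The assumed top removal of 16% of the arm already exceeds the plan's 15% for all losses.

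What stands is that staff may end participation for reasons related to risk and to arm, and that nothing secures outcome collection afterwards.

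**Conclusion.** The concern holds as a gap in the plan that should be fixed. Sections 3.3.1 and 3.3.2 allow removal from the study for injury, PCP-advised suspension or discretion without providing active follow-up, and leave unclear whether record and claims capture applies. The risk is informative, arm-differential censoring in favour of exercise. It bears on first SFRIs that follow non-qualifying injuries, PCP suspensions or discretionary removals, and on fall counts and 36-month outcomes.

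On the stated assumptions the size is modest: a rate ratio of about 0.93 to 0.975 when the truth is 1, and a false-benefit chance of roughly 3.4% to 5.8% instead of 2.5%. The planned relative risk reduction is 46%, so this bias alone would not produce the hypothesised effect. Effective record and claims searches of withdrawn people would shrink it towards zero. A higher or more selective removal rate would enlarge it.

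**What to change.** 1. **Section 3.3.1.** Separate stopping the exercise sessions from leaving the study. Leave the decision about exercising as it is. State that outcome follow-up does not end for injury, PCP-advised suspension or investigator discretion.
2. **Both arms.** Continue the 4-month calls, the 12-, 24- and 36-month assessments and record and claims retrieval to month 36, unless the participant withdraws consent for them.
3. **Section 3.3.2.** Offer people who ask to leave the option of stopping contact while keeping record and claims follow-up.
4. **Sections 8.2 and 8.3.** Name withdrawn participants in the sentence on the record search.
5. **Analysis and reporting.** Report removals by arm and reason, and add a sensitivity analysis for differential withdrawal.

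The cost is a short protocol amendment and consent wording. The calls and assessments are already on the 36-month schedule. The documents contain no study budget, so the cost of continuing them for withdrawn people cannot be priced here.
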